### 5.3 Study Site and Study Population

**5.3.1 Study site:** From July 1, 2025 to December 31, 2025, the subjects were recruited in the inpatient department of endocrinology department of the Eighth Affiliated Hospital of Sun Yat-sen University according to the inclusion and exclusion criteria.

**5.3.2 Study population:** patients with type 2 diabetes and chronic kidney disease (DKD) (n=270)

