### (3) Follow-up in the Queue:

- 1) follow-up time: 3 years after discharge.
- 2) Follow-up methods: outpatient follow-up, telephone follow-up and review of relevant medical records.
- 3) Outcome measures:

**① Primary end point:** progression of DKD. Progression of DKD was defined as renal failure (requiring transplantation or dialysis, or persistent eGFR <15 ml/min/1.73 m^2) or a persistent decline of 30% in eGFR from baseline.

**② Secondary End Points:** I. Cardiogenic Death: Death caused by cardiac disease or related complications. II. Major Adverse Cardiovascular Events (MACE): Including major cardiovascular events such as myocardial infarction, stroke, and unstable angina. III. Kidney Transplantation: Successful cases of kidney transplantation surgery. IV. Hypoglycemic Events: Record the frequency and severity of hypoglycemia occurrences.

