#### **(5) Construction and Evaluation of Forecasting Model**

First, feature screening was performed using LASSO regression to select variables from five aspects: demographic characteristics, baseline scales, gut microbiota and non-target metabolites, and peripheral blood inflammatory biomarkers. Nine machine learning algorithms were employed to construct classification models, with performance evaluated through resampling training/verification mechanisms. The optimal model was selected via 10-fold cross-validation and performance metrics. Model performance and applicability were assessed using AUROC curves, calibration curves, Brier scores, and decision analysis plots. During training, validation, and testing phases of the optimal model, five-fold cross-validation and learning curves were used to evaluate model fit and stability. Finally, SHAP package was utilized to generate SHAP explanation plots to determine the importance and contribution of individual features.

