### 5.8.2 Statistical Analysis

Descriptive statistical analysis was performed on the collected data. Continuous variables were presented as mean  $\pm$  standard deviation (or median and interquartile range), while categorical variables were expressed as frequency and percentage. For intergroup comparisons of continuous variables, independent samples t-test or Mann-Whitney U-test was selected based on data normality. In cases involving multiple group comparisons, one-way ANOVA or Kruskal-Wallis test was employed. Categorical variable comparisons utilized chi-square test or Fisher's exact test to assess significant differences between groups. To evaluate relationships among multiple variables, linear regression was applied to continuous variables, logistic regression to categorical variables, and Cox proportional hazards regression to time-to-event data. These analyses adjusted for potential confounders such as age, sex, disease duration, and baseline glucose levels to ensure result accuracy and reliability. Confounding factors were included in regression analyses to minimize their impact. Additionally, propensity score matching was used to balance baseline characteristics between groups, ensuring comparability and enhancing the internal validity of the study results.

After adjusting for various covariates, we examined the association between adverse prognosis, hyperglycemic variability, and the gut microbiota  $\alpha$ -diversity index. The relationship between hyperglycemic variability, adverse prognosis, and  $\beta$ -diversity differences was tested using genus-level Bray-Curtis distance-based permutation ANOVA (PERMANOVA). Using MaAsLin, we identified gut microbiota communities potentially associated with adverse prognosis and hyperglycemic variability by comparing hyperglycemic variability groups with hypoglycemic variability groups, and prognostic favorable groups with unfavorable groups. OPLS-DA was employed to identify target metabolites potentially related to hyperglycemic variability and adverse prognosis, with adjustments made through linear regression. Mediation analysis was conducted to evaluate whether gut microbiota metabolism might mediate the association between hyperglycemic variability and adverse prognosis. Sensitivity analysis was performed to test the robustness of the mediation effect.

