Based on baseline data, gut microbiota, serum metabolites, and inflammatory factors, predictive models will be constructed using machine learning algorithms (e.g., random forests, support vector machines, neural networks). Feature selection methods (e.g., LASSO regression, recursive feature elimination) will be employed to identify the most prognostic features, thereby enhancing model accuracy and interpretability. Internal stability of the models will be assessed through 10-fold cross-validation, while their generalization ability will be validated using independent validation cohorts.

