January 2028-December 2028	
Main content of the stage goal:
 
① Follow-up Data Organization and Analysis: Conduct comprehensive final organization and analysis of collected follow-up data to ensure data integrity and accuracy. Perform statistical analysis to evaluate patient outcomes, including disease progression, major adverse cardiac events (MACE), quality of life assessment, and complication occurrence. Complete the follow-up data analysis report.
 
② Association Analysis: By integrating glycemic variability grouping results, this study investigates the relationship between gut microbiota characteristics and serum metabolite profiles with clinical outcomes, including disease progression, major adverse cardiovascular events (MACE), quality of life, short-term complications, and overall prognosis. Through correlation analysis and multiple regression analysis, we aim to uncover underlying biological mechanisms and predictive biomarkers, ultimately producing a comprehensive association analysis report.
 
③ Prediction Model Development: By integrating multi-dimensional data including baseline information, gut microbiota profiles, serum metabolite profiles, and inflammatory factors, we constructed predictive models using machine learning algorithms such as random forests, support vector machines, and neural networks. Through cross-validation and other optimization methods, we enhanced the model's predictive performance and stability, completing the initial development of the prediction model.
 
④ Model evaluation and validation: Appropriate evaluation metrics were used to assess the constructed prediction model, verifying its generalization capability and predictive performance across different datasets. Based on the evaluation results, the model was further optimized and adjusted to ensure reliability and practicality, and the model evaluation report was completed.
 
Achievement :
 
 
① The follow up data analysis report was completed.
 
② Complete the association analysis report.
 
③ The preliminary construction of the prediction model was completed.
 
④ The model evaluation report was completed.
 

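### Binary prediction models are to be built and evaluated during 2028, while modelling patients are still completing their 3 years, with no stated horizon or allowance for incomplete follow-up

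*Protocol*

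**What the plan says.** Method. Section 5.5 (5) of the protocol states: "Nine machine learning algorithms were employed to construct classification models". It adds: "Model performance and applicability were assessed using AUROC curves, calibration curves, Brier scores, and decision analysis plots". Section 5.8.2 names three types of learner as examples, none in a survival form. The same section assigns "Cox proportional hazards regression to time-to-event data", but in the association analyses, not in the prediction modelling.

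Outcome. Sections 3.1 and 5.5 (3) make progression of kidney disease the primary endpoint: renal failure "or a persistent decline of 30% in eGFR from baseline". Section 3.2.1, the prediction-model objective, lists all-cause death as its primary endpoint instead.

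Timing. Section 5.3.1: "From July 1, 2025 to December 31, 2025, the subjects were recruited". Section 5.5 (3): "follow-up time: 3 years after discharge". In Section 9, the January to December 2028 stage contains the final work on follow-up data, the association analysis, model building ("completing the initial development of the prediction model") and the model evaluation report. Validation patients are recruited from January to May 2026, and the model is tested on them in January to July 2029.

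**The concern.** A yes/no classifier needs a known class for each patient. For an outcome that accrues over 3 years, the class is known once the patient has had the event or has been observed without it for the full 3 years. A patient who is event-free at 2.5 years has no 3-year class yet. The protocol recognises time-to-event data in its association analyses, but fixes ordinary classification and ordinary performance measures for the models and schedules that work while follow-up is still running.

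What is at stake is the absolute risk that the model reports. Unfinished patients coded as non-events pull predicted risk down. Unfinished patients dropped, while early events are kept, push it up. Calibration curves and Brier scores computed on the same incomplete classes would not reveal either error.

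**Working it through.** **Calendar.** Recruitment from 1 July to 31 December 2025 plus 3 years gives 1 July to 31 December 2028, counted from enrolment. Section 5.5 (3) counts from discharge, which moves the end to about January 2029. The 2028 stage therefore opens with every modelling patient at 2.0 to 2.5 years and closes about when the last one completes.

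**The plan's own figure.** Section 5.4 cites 156 progression events in 975 patients over a mean of 4.7 years and requires 30 events: 975/156 × 30 = 187.5, which reproduces exactly. A 10% allowance gives 187.5 × 1.10 = 206.25 or 187.5/0.90 = 208.3, both close to the stated 210.

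**Assumptions for what follows.** Progression is the outcome; constant hazard; uniform accrual of 210 patients; events known when they occur; follow-up capped at 3 years.

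- Hazard: −ln(1 − 156/975)/4.7 = −ln(0.84)/4.7 = 0.0371 per year.
- 3-year risk: 1 − exp(−0.0371 × 3) = 10.53%, so 210 × 0.1053 = 22.1 events.
- Events seen at a cut: the sum over patients of 1 − exp(−0.0371 × follow-up). On 1 January 2028 the mean risk is about 8.0%, or 16.8 events.

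| Data cut | Follow-up (years) | Patients at 3 years | Events seen | 3-year events not yet seen |
|---|---|---|---|---|
| 1 Jan 2028 | 2.0–2.5 | 0% | 16.8 | 5.3 (24%) |
| 1 Jul 2028 | 2.5–3.0 | about 1% | 20.4 | 1.7 (8%) |
| 1 Oct 2028 | 2.75–3.0 | 51% | 21.7 | 0.4 (2%) |
| 31 Dec 2028 | 3.0 | about 100% | 22.1 | near 0 |

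With an assumed 14-day lag from enrolment to discharge, the unseen events are 5.6, 2.0, 0.6 and near 0, and 0%, 0%, 43% and 93% of patients have reached 3 years. The 24% depends little on the rate: if risk simply rose in proportion to time, the share at the January cut would be 1 − 2.25/3 = 25%.

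**Direction of bias, taking the 1 October 2028 cut.** About 92.6 patients are event-free but short of 3 years.

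- Coded as non-events: 21.7/210 = 10.3%, against a true 10.5%.
- Dropped: 21.7/(210 − 92.6) = 21.7/117.4 = 18.5%.

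On 1 July, coding gives 20.4/210 = 9.7%, while dropping would leave almost only events: 20.4/(210 − 187.8) = 20.4/22.2 = 92%.

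**Loss to follow-up.** If 10% are lost over 3 years, the loss hazard is −ln(0.9)/3 = 0.0351 per year and the total hazard is 0.0722. If those lost are coded event-free, observed risk is (0.0371/0.0722) × (1 − exp(−0.0722 × 3)) = 10.0%, against 10.5%. About 20 patients are lost.

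**The case against.** The strongest reply is that the protocol fixes no data cut. The 2028 stage lasts 12 months, lists follow-up work before modelling, and calls the model due at its end preliminary. Section 9 also allows adjustments in 2029. A cut on 31 December 2028 would miss almost no events. Horizon and censoring rules can also sit in a statistical analysis plan that is not shown. This stands to the extent that the 24% is a worst case, tied to a cut on the first day of the stage. It does not remove the conflict: the same stage must deliver the follow-up report, the association report, the model and its evaluation by December 2028, and a year-end cut leaves no time for any of them. That clash lies within the protocol.

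A reader might infer more than the documents support:

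- That unfinished patients are labelled event-free. No section says so. They could equally be dropped or weighted.
- That all model building precedes 3 years. Patients begin to complete in July 2028, inside the stage.
- That classifiers cannot be used. Classification at a fixed, fully observed 3-year horizon is valid, and censoring weights extend it to patients lost earlier.
- That validation comes too early. Those patients reach 3 years between January and May 2029, within a stage that runs to July 2029.
- That the 10% dropout allowance rivals the event count. About 20 lost patients at 10.5% risk carry only about 2 events.

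The follow-up completeness target above 95% in Section 9 does not settle the matter. It belongs to a stage ending in December 2027, before any patient can have 3 years.

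**Conclusion.** The concern holds in this limited form: the method is plain binary classification, and the 2028 dates cannot all be met on complete 3-year outcomes. At a cut between January and October 2028, about 24% falling to 2% of 3-year progression events would be unseen. If unfinished patients are dropped rather than coded as non-events, the upward bias is larger, and it shrinks more slowly as the cut is moved later. Loss to follow-up alone is a minor issue.

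The counts rest on a constant hazard from the cited cohort, uniform accrual, and progression as the outcome. If the model predicts all-cause death, as Section 3.2.1 says, the timing conflict is the same, but the documents give no death rate from which to count events. The matter should be corrected before modelling starts; it does not undermine the cohort itself.

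**What to change.** 1. Define the model outcome as status at 3 years, and say whether it is progression or all-cause death, reconciling Section 3.2.1 with Sections 3.1 and 5.5 (3).
2. Lock the modelling data only after the last modelling patient's 3-year visit (about January 2029), and move the Section 9 dates for model building and evaluation accordingly. This alone removes the problem of unfinished follow-up.
3. For patients lost before 3 years, use inverse-probability-of-censoring weights, and report AUC, Brier score and calibration at 3 years with the same weights. Survival versions of the learners are an acceptable alternative, not a requirement.
4. Treat death as a competing event only if progression is the predicted outcome.

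The cost is new wording, standard software and a short shift of work into the 2029 stage, which already holds validation and reporting. Any of the nine algorithms that cannot take weights may have to be dropped.

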#### **5.6 Experimental Scheme**

Step	Period	Filter period	Period of wearing CGM			Follow-up period		
	Study follow-up	Visit 0	Visit 1	Visit 2	Visit 3	Visit 4	Visit 5	Visit 6
	Study date (days)	1 day before enrollment	1 day after enrollment	7 days after enrollment	14 days after enrollment	Within 1 year after enrollment	Within 2 years after enrollment	Within 3 years after enrollment

1	Selection and exclusion criteria	✓						
2	Sign the informed consent form.	✓						
3	Adorn CGM		✓					
4 clinical data	Basic information of the subjects		✓					
	Clinical diagnosis		✓					
	Personal history		✓					
	History of past illness		✓					
	Check-up		✓					
5 clinical examination Inspection	Routine blood test			✓				
	Liver function			✓				
	Renal function			✓				
	HbA1c			✓				
	Blood fat			✓				
	Fasting insulin (FIns)			✓				
	Blood sugar			✓				
	Thyroid function			✓				
	Coagulation function			✓				
6	Medication during CGM monitoring				✓			
7	Fecal collection		✓					
8	Blood collection		✓					
9	Medications taken after discharge				✓			

10	Download the CGM report				✓			
11	Fecal microbiota sequencing					✓		
12	Metabolite assay in serum					✓		
13	Progression events of DKD during follow-up					✓	✓	✓
14	Assessment of MACE events during follow-up					✓	✓	✓
15	Death events during follow-up		✓	✓	✓	✓	✓	✓
16	Adverse event monitoring		✓	✓	✓			
17	Deviation from plan record		✓	✓	✓	✓	✓	✓
18	Fill in CRF		✓	✓	✓	✓	✓	✓

## 5.7 Collection, Storage, Use, and Destruction of Research Data and / or Biological Samples

### 5.7.1 STUDY DATA

**Data Collection:** This study will collect participants' age, gender, education level, medical history, medication history, and physical measurements including height, weight, blood pressure (BP) (systolic [SBP] and diastolic [DBP]), waist circumference (WC), hip circumference (HC), and waist-to-hip ratio (WHR) through face-to-face interviews, physical examinations, and continuous glucose monitoring (CGM) tests. The CGM will also collect real-time blood glucose data.

**Storage:** The above information is stored in the medical information platform of our hospital.

**Use:** All data collected in this study are used for clinical research data analysis and will not be used for commercial purposes.

**Destruction:** The study will be destroyed in accordance with the regulations 5 years after the study is completed.

### 5.7.2 Biological Specimen

**DATA COLLECTION:** Blood and stool samples were collected from the participants and analyzed for complete blood count, liver function, kidney function, glycated hemoglobin, blood lipids, fasting insulin, thyroid function, coagulation function, and gut microbiota.

**Storage:** All the specimens were stored in the biological sample bank of our hospital.

**Use:** All data collected in this study are used for clinical research data analysis and will not be used for commercial purposes

road .

Destruction: The study will be destroyed in accordance with the regulations 5 years after the study is completed.

## **5.8 Data Management and Statistical Analysis Plan:**

### **5.8.1 Data Management**

#### **5.8.1.1 Data Collection Methods and Procedures:**

- (1) Data collection tools: Electronic Case Report Form (CRF)
- (2) The baseline data were collected during the hospitalization of the patients, and the follow-up data were collected at 1, 2 and 3 years.
- (3) Collection: Researcher
- (4) Data quality control: Training before data collection, focusing on instructions and quality monitoring

#### **5.8.1.2 Data Reception Method and Process:**

- (1) Data reception method: paper or spreadsheet
- (2) Reception time and frequency: Send in real time to the general manager for summary
- (3) Recipient: Researchers
- (4) Data review: Each CRF must be reviewed and approved by the responsible person before consolidation

#### **5.8.1.3 Data Entry Method and Process:**

- (1) Input tool: Professional data entry software
- (2) Entry person: Researcher
- (3) Entry time and frequency: Enter immediately after completing each CRF
- (4) Data quality check: Quality control is performed after data entry to ensure accuracy and reasonableness

#### **5.8.1.4 Data Management Process:**

- (1) data collection: researchers collected clinical data, stool, and serum samples according to standard protocols
- (2) Data reception: After each CRF form is reviewed and approved, it is stored in the main file repository.
- (3) Data entry: Researchers enter data according to the standard
- (4) Data cleaning: After data entry, perform quality control and review to correct and remove non-compliant or duplicate data
- (5) Data storage: Data is stored in password-protected electronic storage devices and managed with specialized database software
- (6) Data backup: Back up data regularly

(7) Data access: Set permission levels to control data access and ensure security

(8) Security: Storing data in public areas is prohibited to ensure data confidentiality

### 5.8.2 Statistical Analysis

Descriptive statistical analysis was performed on the collected data. Continuous variables were presented as mean  $\pm$  standard deviation (or median and interquartile range), while categorical variables were expressed as frequency and percentage. For intergroup comparisons of continuous variables, independent samples t-test or Mann-Whitney U-test was selected based on data normality. In cases involving multiple group comparisons, one-way ANOVA or Kruskal-Wallis test was employed. Categorical variable comparisons utilized chi-square test or Fisher's exact test to assess significant differences between groups. To evaluate relationships among multiple variables, linear regression was applied to continuous variables, logistic regression to categorical variables, and Cox proportional hazards regression to time-to-event data. These analyses adjusted for potential confounders such as age, sex, disease duration, and baseline glucose levels to ensure result accuracy and reliability. Confounding factors were included in regression analyses to minimize their impact. Additionally, propensity score matching was used to balance baseline characteristics between groups, ensuring comparability and enhancing the internal validity of the study results.

After adjusting for various covariates, we examined the association between adverse prognosis, hyperglycemic variability, and the gut microbiota  $\alpha$ -diversity index. The relationship between hyperglycemic variability, adverse prognosis, and  $\beta$ -diversity differences was tested using genus-level Bray-Curtis distance-based permutation ANOVA (PERMANOVA). Using MaAsLin, we identified gut microbiota communities potentially associated with adverse prognosis and hyperglycemic variability by comparing hyperglycemic variability groups with hypoglycemic variability groups, and prognostic favorable groups with unfavorable groups. OPLS-DA was employed to identify target metabolites potentially related to hyperglycemic variability and adverse prognosis, with adjustments made through linear regression. Mediation analysis was conducted to evaluate whether gut microbiota metabolism might mediate the association between hyperglycemic variability and adverse prognosis. Sensitivity analysis was performed to test the robustness of the mediation effect.

Based on baseline data, gut microbiota, serum metabolites, and inflammatory factors, predictive models will be constructed using machine learning algorithms (e.g., random forests, support vector machines, neural networks). Feature selection methods (e.g., LASSO regression, recursive feature elimination) will be employed to identify the most prognostic features, thereby enhancing model accuracy and interpretability. Internal stability of the models will be assessed through 10-fold cross-validation, while their generalization ability will be validated using independent validation cohorts.

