#### 4.1.3. Gut Microbiota and Serum Metabolites in DKD Patients with Different Blood Glucose Variability Groups and Their Correlation with Prognosis

(1) Patients with DKD were divided into high GV group and low GV group according to GV status, and the intestinal microbiota characteristics and serum metabolites characteristics of patients in different GV groups were analyzed.

(2) Based on the association between gut microbiota, serum metabolic biomarkers and prognosis, the relationship between the bacterial co-abundance group (CAG) and the functional modules of serum metabolites was further established to explore their correlation with glycemic variability and poor prognosis.

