## 5.4 Methods for Determining the Required Sample Size for Research

This exploratory study investigates the impact of gut microbiota and related metabolites on prognosis in diabetic kidney disease (DKD) patients. To achieve this, patients will be divided into two groups based on adverse prognosis outcomes, with subsequent comparisons of gut microbiota and metabolite differences between groups. To minimize microbial variations caused by individual differences, each group requires at least 30 participants, meaning there must be at least 30 patients with adverse prognosis events. Drawing from existing research, a 2023 study published in *\*Diabetes Care\** [Diabetes Care.2023;46(4):868-873.] included 975 DKD patients with an average follow-up of 4.7 years, reporting 156 major outcomes of DKD progression. Consequently, the total sample size was calculated as  $975/156*30=187.5$ . Considering potential dropouts and incomplete responses, we typically increase the sample size by 10%, ultimately enrolling 210 patients as the modeling cohort. Additionally, 60 DKD patients were included as a validation cohort. During actual recruitment, sample size adjustments may be made based on factors such as recruitment speed and data quality. Regular assessments of sample adequacy should also be conducted to ensure statistical power.

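### PERMANOVA is the only beta-diversity test named; with prognosis groups as unequal as the plan implies, it cannot separate a shift in composition from a difference in spread

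*Protocol*

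**What the plan says.** Protocol section 5.8.2 says of beta-diversity that "differences was tested using genus-level Bray-Curtis distance-based permutation ANOVA (PERMANOVA". The test is applied to adverse prognosis and to glycemic variability (GV). No test of dispersion and no statistic that allows unequal spread is named beside it.

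Section 5.4 divides patients by prognosis and sets a floor: "each group requires at least 30 participants, meaning there must be at least 30 patients with adverse prognosis events". It takes its event rate from a published cohort that "included 975 DKD patients with an average follow-up of 4.7 years, reporting 156 major outcomes of DKD progression", allows for dropout ("we typically increase the sample size by 10" per cent), and arrives at "ultimately enrolling 210 patients as the modeling cohort". Section 5.5 (3) sets "follow-up time: 3 years after discharge".

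For GV, section 4.1.3 states "Patients with DKD were divided into high GV group and low GV group according to GV status", without cut-points or group sizes. For continuous variables, section 5.8.2 says "independent samples t-test or Mann-Whitney U-test was selected based on data normality", without saying which form of the t-test.

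**The concern.** The study wants to know whether the gut community of patients who do badly differs from that of patients who do well. Random relabelling produces the null hypothesis that both groups come from the same distribution, with equal centre and equal spread. The pseudo-F statistic pools the within-group variation. With equal group sizes it is nearly insensitive to unequal spread. With very unequal sizes it is not: it over-rejects if the small group is more variable and under-rejects if the small group is tighter.

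A significant result could therefore mean only that the few adverse patients differ more among themselves, and still be reported as a distinct adverse-prognosis microbiota. In the opposite case a real shift could be missed. With no dispersion result alongside, the reader could not tell which had happened.

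**Working it through.** **Group sizes (section 5.4).** The plan's own figure reproduces: 975/156 × 30 = 187.5. Dividing by 0.9 gives 208.3, so 209; multiplying by 1.1 gives 206.25, so 207. Both are close to 210. The source rate is 156/975 = 16%. The possible splits are:

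- 30 events in the 187.5 patients left after dropout: 30 against about 158.
- 16% of all 210: 33.6, so 34 against 176.
- Exactly the floor of 30 among 210: 30 against 180.
- 16% at 4.7 years scaled to 3 years at constant hazard: 1 − 0.84^(3/4.7) = 10.5%, so 22 against 188.

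**Assumptions.** The documents do not give the significance level, the spread ratio, the effective dimension or the effect size for this test. I take 5%, a ratio of standard deviations (SDs) of 1.25, 1 to 50 independent Gaussian axes, and Euclidean distances, for which equal centroids hold exactly.

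**Expected pseudo-F with equal centroids.** With sizes n1 and n2 and variances s1² and s2²:

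R = (n2·s1² + n1·s2²) / (n1·s1² + n2·s2²)

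- 30 against 180, small group wider (1.25² = 1.5625): R = (281.25 + 30)/(46.875 + 180) = 1.37.
- 30 against 180, small group tighter (0.8² = 0.64): R = (115.2 + 30)/(19.2 + 180) = 0.73.
- Equal sizes: R = 1 for any variances.

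**Rejection rates.** In large samples, the rate under no shift is P(χ²_p > c/R), where c is the 95% point on p degrees of freedom. At p = 10, c = 18.31 and c/1.37 is about 13.3, giving 20.5%. For power, the shift is set to give 80% when spreads are equal.

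| Effective dimensions p | 1 | 2 | 5 | 10 | 20 | 50 |
|---|---|---|---|---|---|---|
| Small group wider, no shift: rejects | 9% | 11% | 15% | 20.5% | 29% | 50% |
| Small group tighter (0.8): power, from 80% | 86% | 85% | 82% | 77% | 70% | 50% |

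Permutation simulation with the small group wider gave 10.7%, 21.8% and 47.6% at p = 2, 10 and 50. With 105 against 105 it gave 4.6%, 5.0% and 4.5%. At p = 10 the splits of 30/158 and 34/176 give about 19%, and 22/188 gives 23%.

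The power row compares PERMANOVA with itself under equal spread. That flatters it, because a tighter group means less noise and a correctly sized test should gain. Against a Welch-type distance test (Wd*) on the same data (10 axes, ratio 0.8, shift of 0.8 of the adverse group's SD), power was 46.7% against 73.7%. Repeat runs gave 46.0% against 75.4%, and 43% against 72%. That gap of 27 to 29 points also depends on dimension: 6, 17, 41 and 38 points at 2, 5, 20 and 50 axes.

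**On the protocol's own metric.** These are Dirichlet-multinomial counts for 80 genera with equal mean composition and Bray-Curtis distances, at 30 against 180:

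| Mean within-group distance, adverse vs favourable | PERMANOVA rejects | Wd* rejects |
|---|---|---|
| 0.65 vs 0.60 | 22% | 12% |
| 0.77 vs 0.72 | 28.5% | 16% |
| 0.73 vs 0.77 (large group wider) | 7% | 15% |

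On Bray-Curtis distances a change in spread also moves the centroid, so no test here isolates composition cleanly.

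**The t-test.** With one variable, the pooled form has a true error of 9.5% at an SD ratio of 1.25 and 14.0% at 1.5, if the small group is the more variable.

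**The case against.** The strongest reply is that the protocol states nothing false. It speaks of beta-diversity differences and never claims a test of centroids only. A companion dispersion test is the kind of detail often left to a statistical analysis plan, which is not shown. The study calls itself exploratory, and its prognosis comparison also rests on alpha-diversity and MaAsLin. The Cox and prediction analyses do not use PERMANOVA. Most of this stands: it limits the weight of the point and rules out calling PERMANOVA an error. It does not remove the ambiguity in reading the one beta-diversity test that the protocol names.

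Three stronger readings are tempting, and the documents support none of them.

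- A reader might infer that 30 against 180 is the planned split. Section 5.4 gives 30 as a minimum, and 180 is only a subtraction. The nearby splits lead to the same conclusion.
- A reader might take 20% false positives or 27 points of lost power as properties of this design. Both depend on an assumed spread ratio and about 10 effective dimensions, and the 27 points also on the comparator.
- A reader might conclude that Wd* should replace PERMANOVA. On Bray-Curtis distances Wd* also over-rejects when spreads differ, and it did worse than PERMANOVA with the large group wider. A two-group Wd* also does not adjust for covariates, while section 5.8.2 stresses confounder adjustment.

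Nor does the protocol say that its t-test is the pooled one. Propensity score matching could even out the groups, but section 5.8.2 does not tie it to PERMANOVA.

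**Conclusion.** The point holds in a limited form. At the imbalance implied by section 5.4, a significant PERMANOVA by prognosis cannot be read as a difference in composition alone. If the adverse group is 1.25 times as variable, the false-positive rate for a composition shift is about 9% to 50% across 1 to 50 effective dimensions, and about 20% at 10. If the adverse group is tighter, the result ranges from no loss to a substantial loss of power. These figures assume Gaussian data and Euclidean distances; the Bray-Curtis checks agree in direction but not in exact size. Nothing in the documents says which group will be more variable, or that spreads will differ at all. With near-equal groups, such as a median GV split or a matched set, both effects largely disappear.

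**What to change.** In section 5.8.2:

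- Keep PERMANOVA, with covariates, as the main beta-diversity test.
- Report PERMDISP on the same genus-level Bray-Curtis matrix beside it, for the prognosis comparison and for any GV comparison with unequal group sizes.
- State that when PERMDISP shows unequal spread, a significant PERMANOVA will be reported as a difference in composition and/or heterogeneity, not attributed to composition alone.
- Allow Wd* as a sensitivity analysis only, neither replacing PERMANOVA nor serving as the sole basis for a composition claim.
- Where a t-test compares the unequal prognosis groups, specify the Welch form.

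If a separate analysis plan already contains these steps, a cross-reference is enough. The cost is a few lines of text and code on an existing matrix, with no new patients, samples or assays, and more guarded wording when spreads differ.
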